1.2 Study design

This is a multicentre, multinational, randomised, open-label, reader-blinded, dose-confirmation, 2 × 3 factorial phase II study, with an approximate 7-week duration.

Two target peptide mass dose ranges (5-20 µg and 30-45 µg), and three radioactivity dose ranges (40-80 megabecquerels [MBq], 100-140 MBq and 160-200 MBq activity of ⁶⁸Ga) of ⁶⁸Ga-OPS202 will be investigated to provide information on different possible peptide/radioactivity dose range combinations that are summarized in table below.

[figure not shown]
Table 1 Combinations of studied peptide mass dose ranges and radioactivity dose ranges

Peptide mass dose range	Radioactivity dose range		
	40-80 MBq	100-140 MBq	160-200 MBq
5 – 20 µg	8 scans	8 scans	8 scans
30 – 45 µg	8 scans	8 scans	8 scans

Each of the 24 evaluable subjects will receive two different peptide/radioactivity ranges combinations
Hence, 48 PET/CT scans will be analysed (8 in each combination peptide/radioactivity dose range)

Subjects will be assigned to one of three study arms (see [Figure 1](#)). At the end of the study, each subject will provide two sets of images corresponding to two combinations of peptide / radioactivity dose ranges. The sets of images will be sent to an imaging core lab (ICL) for central blinded reading by two independent experienced radiologists and a third for adjudication of discordances. The readers will be specifically trained for this protocol.

Figure 1 Study Design and Subject Allocation

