3.1.5 Significance testing and estimation

The statistical analysis of efficacy and safety is descriptive, therefore no formal statistical significance testing will be performed.

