3.2.1.2 Secondary efficacy analysis

All secondary and exploratory analyses will be performed on PP population only.

Selection of the optimal dose range for peptide mass and radioactivity of ^{68}Ga -OPS202 will be based on the provided descriptive statistics for all secondary and exploratory efficacy endpoints, in addition to primary endpoint.

Key Secondary Endpoint:

a) Image quality

Quantitative measure:

For each PET assessment, image quality will be quantitatively measured by the tumour-to-background ratio, which will be obtained using the mean of all lesions tumour-to-backgrounds, for each of the four following organs:

- Liver
- Lymph nodes
- Bone
- Lungs

For up to five most avid lesions per organ that are confirmed by SOT, the tumour-to-background ratio will be computed as lesion SUV_{mean} divided by the SUV_{mean} of the subject's reference tissue (tumour-free liver or aortic blood).

Tumour-to-background ratio is a unit-less measure. A high tumour-to-background ratio indicates high effectiveness of ^{68}Ga -OPS202 as a diagnostic agent.

Tumour-to-background ratio will be analysed using descriptive statistics, presented for each of the four organs and for:

- each of the six combinations of injected peptide/radioactivity dose range
- each of the two peptide mass dose ranges
- each of the three radioactivity dose ranges

Individual values of tumour-to-background ratio will be listed by subject, by organ and by visit. Background location will be specified (L: Liver, B = Aortic blood).

Qualitative measure:

A qualitative analysis of the image assessed by the independent blinded readers will be performed to back up the quantitative quality measured by tumour-to-background analysis. This qualitative assessment will be performed using a quality score.

For each PET/CT and PET assessment, each independent blinded reader will perform a direct comparison of the two ^{68}Ga -OPS202 scans (Visit 2 and Visit 3, that have with different peptide and radioactivity doses). He/she will note which of the pair provides superior images based on overall image quality and lesion count, attributing a score for each assessment.

The score for the assessment having superior images will be set to “1”, and score for the assessment not selected will be set to “0”. In case of equal quality, both assessments will have a score of “1”.

Values will be available in the database provided by ICL.

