3.2.17 Covariates and analysis of subgroups

It is not planned to perform such analysis.

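### The key secondary tumour-to-background ratio pools liver- and blood-referenced values in one summary, which can distort comparisons between arms' cells and between radioactivity ranges

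*SAP*

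**What the plan says.** SAP 3.2.1.2 a) takes up to five of the most avid confirmed lesions per organ and divides each lesion's SUVmean by the SUVmean of the subject's "reference tissue (tumour-free liver or aortic blood". The organ value for a scan is "obtained using the mean of all lesions tumour-to-backgrounds, for each of the four following organs".

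On reporting, the SAP states: "Tumour-to-background ratio will be analysed using descriptive statistics, presented for each of the four organs and for" the six dose cells, the two peptide ranges and the three radioactivity ranges. Reference tissue is not among the groupings. It appears in the individual listing: "Background location will be specified (L: Liver, B = Aortic blood".

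Selection of the dose range, under the same section, "will be based on the provided descriptive statistics for all secondary and exploratory efficacy endpoints, in addition to primary endpoint". SAP 3.2.17, on covariates and subgroups, says "It is not planned to perform such analysis". SAP 3.1.5 adds: "The statistical analysis of efficacy and safety is descriptive, therefore no formal statistical significance testing will be performed".

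The protocol names no background tissue for this endpoint. Sections 7.2 and 7.3 refer to the imaging review charter for the calculation.

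The exploratory SUVmax ratio (SAP 3.2.1.2 g, restated in SAP 5) is defined on tumour-free liver, and item h) is headed as an SNR in the liver. The listings for both nevertheless carry the same liver/aortic-blood legend.

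**The concern.** A lesion-to-liver ratio and a lesion-to-blood ratio are on different scales unless liver and blood happen to have the same SUVmean. The protocol itself, in its preclinical background (section 1.1), names tumour-to-blood and tumour-to-liver as separate quantities. The SAP puts both into one column.

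No test or interval is planned, so the dose cells are compared on their descriptive statistics alone. Cells are small, and an organ cell can be smaller than 8 because only subjects with confirmed lesions in that organ contribute. If blood-referenced subjects are spread unevenly over the arms, part of the apparent ranking of dose ranges on this endpoint could reflect the choice of denominator rather than the dose.

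**Working it through.** **Layout.** SAP 1.2: "Each of the 24 evaluable subjects will receive two different peptide/radioactivity ranges combinations". So 24 × 2 = 48 scans; 48/6 = 8 per cell, 48/2 = 24 per peptide range, 48/3 = 16 per radioactivity range. This reproduces the SAP's 48 scans and 8 per cell.

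**Which cells share subjects** (protocol 6.1.1). Visit 2 is always 5-20 µg and Visit 3 always 30-45 µg.

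- Arm A: 40-80 MBq, then 100-140 MBq.
- Arm B: 100-140 MBq, then 160-200 MBq.
- Arm C: 160-200 MBq, then 40-80 MBq.

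**Effect of the denominator.** Let k = liver SUVmean / blood SUVmean. For any lesion, lesion/blood = (lesion/liver) × k. The factor carries through the mean over lesions. If m of n subjects in a cell are blood-referenced, and on liver they would have averaged the same as the others, the cell mean is multiplied by 1 + (m/n)(k − 1). The shift is therefore (m/n)(k − 1).

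**Inputs not in the documents.** Neither k nor m is given; both are assumptions, shown as ranges. Cell-mean shift with n = 8 and no true dose effect:

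| k | m = 1 | m = 2 | m = 3 |
|---|---|---|---|
| 0.5 | −6.25% | −12.5% | −18.75% |
| 1 | 0 | 0 | 0 |
| 1.5 | +6.25% | +12.5% | +18.75% |
| 2 | +12.5% | +25% | +37.5% |
| 3 | +25% | +50% | +75% |

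If only 4 subjects in the cell have lesions in the organ, the same m doubles every entry.

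**Median.** It moves less. In a simulation with log-normal ratios and an assumed CV of 30% to 50%, 2 of 8 subjects at k = 2 move it by about 13% to 16%.

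**Scale.** With the same assumed CVs, the standard error of a difference between two independent 8-subject cell means is CV × √(2/8), that is 15% to 25% of the mean. The 25% shift at k = 2 is thus about 1 to 1.7 standard errors.

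**Margins.** Two blood-referenced subjects, both in arm A, k = 2:

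- Same tissue at both visits. Radioactivity: 40-80 and 100-140 MBq each rise by (2/16)(2 − 1) = 12.5%; 160-200 MBq does not move. Peptide: both ranges rise by (2/24)(2 − 1) = 8.3%, so no false peptide difference. The two arm A cells also rise equally.
- Blood at Visit 2 only. The low-peptide mean alone rises by 8.3%, and only 40-80 MBq rises, by 12.5%.
- For contrast, one blood-referenced subject in every arm, same tissue at both visits: every cell rises by 12.5% and no dose difference appears. Imbalance is what matters.

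**Chance of imbalance.** Suppose tissue is unrelated to arm and all 24 subjects contribute. The probability that some two arms differ by at least 2 blood-referenced subjects is then hypergeometric:

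- 2 such subjects: 3 × C(8,2)/C(24,2) = 84/276 = 0.30.
- 3: 1 − 8³/C(24,3) = 1 − 512/2024 = 0.75.
- 4: 1 − 3 × 28 × 8 × 8/C(24,4) = 1 − 5376/10626 = 0.49.
- 6: 1 − 28³/C(24,6) = 1 − 21952/134596 = 0.84.

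**After the change.** With one tissue throughout, or with separate summaries by tissue, every ratio in a summary has the same denominator and the artificial shift is 0 for any m and k.

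**The case against.** The strongest reply is that the visible text may not be the whole rule. Protocol 7.3 assigns the calculation of this ratio to the imaging review charter, and SAP Appendices 1 and 2 hold derivations and table templates; none of these is available here. If the charter fixed the tissue by organ, no per-organ cell would mix denominators. This stands as a limit on certainty. But the SAP wording ties the tissue to the subject, the listing expects both, and the SAP's own list of summary groupings contains no split.

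The SAP's reference to a subject's tissue can also be read as one tissue per subject, which would protect the peptide comparison. That is a fair reading, but the SAP does not state it.

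The ratio is also not the only evidence. SAP 3.2.1.1 bases selection on the highest relative lesion counts. Medians, lesion SUVmax (which has no background denominator) and a paired reader quality score are reported too, and the listing would let a careful reader spot an imbalance. All true. These limit the damage, but a listing does not correct the summary.

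Two stronger readings are tempting. A reader might infer that blood-referenced subjects always inflate a cell. The documents do not give k; the shift is zero at k = 1 and negative below it. A reader might also infer from the legend in g) and h) that those measures mix tissues as well. Their definitions specify liver only (SAP 3.2.1.2 g and h, SAP 5, protocol 7.2), so the legend is an inconsistency, not evidence of mixing.

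**Conclusion.** The point holds as a conditional one. Followed as written, SAP 3.2.1.2 a) pools two scales in a summary that feeds dose selection. If some subjects are blood-referenced and they are unevenly spread over the arms, comparisons between cells of different arms and between radioactivity ranges can be distorted with no true dose effect. For 2 of 8 subjects the cell mean moves by between −12.5% and +50% over k = 0.5 to 3. The radioactivity means move by half the cell figure when both subjects are in one arm.

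A reader might extend this to every dose comparison. The documents do not support that: each subject contributes one scan to each peptide range, so with one tissue at both visits, the same k at both, and no true dose effect, both peptide means shift equally. Nor do they show that mixing will occur, or that it would settle the choice of dose. The risk is a misleading descriptive ranking on the key secondary endpoint; as no test is planned, type I error is not at issue.

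**What to change.** In SAP 3.2.1.2 a):

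- Use one reference tissue per organ for all subjects in the main table, where it is available. Otherwise tabulate liver- and blood-referenced ratios separately for the cells and both margins.
- State that a subject has the same tissue at both visits, and word this consistently with the imaging review charter. If the charter already fixes the choice, a sentence saying so is enough.
- Apply the same rule where this ratio is reused in the dose-per-kg plots and tables of item d).

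In g) and h), reconcile the aortic-blood entry in the listing legend with the liver-only definitions.

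The cost is SAP wording and a table split. Location is already recorded, so the split needs no new data; a single common tissue may need further background measurements if only one was taken per subject, which the documents do not say. The downside of splitting is smaller n within each location, with some organ cells down to very few subjects. Those rows should show their n and be read accordingly.

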Quality score will be analysed using descriptive statistics (frequencies and percentage), presented for:

- each of the six combinations of injected peptide/radioactivity dose range
- each of the two peptide mass dose ranges
- each of the three radioactivity dose ranges

Two sets of analysis will be performed for quality score:

- Based on assessment by reader A
- Based on assessment by reader B

Besides, readers scores will also be summed up together and presented for each of the six combinations of injected peptide/radioactivity dose range.

Individual values of quality score as well as which scan do reader prefer and reason for selecting scan 2 or 3 will be listed per reader, then by subject and by visit for both types of assessment (PET/CT and PET).

Other Secondary Endpoints:

b) Lesion SUV_{max}

For each PET assessment, lesion SUV_{max} (unit-less measure) will be measured for each lesion, up to a maximum of five most avid lesions per organ that are confirmed by SOT. In order to obtain a unique measure per organ, mean of the SUV_{max} will be computed within each of the four following organs:

- Liver
- Lymph nodes
- Bone
- Lungs.

Values will be available in the database provided by ICL.

Lesion SUV_{max} will be analysed using descriptive statistics, presented per organ and for:

- each of the six combinations of injected peptide/radioactivity dose range
- each of the two peptide mass dose ranges
- each of the three radioactivity dose ranges.

Individual values will be listed by subject, by organ and by visit.

- c) Absolute number of lesions detected by ^{68}Ga -OPS202, both as standalone and also compared to SOT

For each PET/CT and PET assessment, the number of lesions detected by ^{68}Ga -OPS202 and by SOT will be reported for each of the five following anatomic sites:

- Primary site of GEP-NET
- Lymph nodes
- Liver
- Axial/appendicular skeleton (Bones)
- Lungs

Values will be available in the database provided by ICL.

Absolute number of lesions detected by ^{68}Ga -OPS202 and difference with number of lesions detected by SOT will be analysed using descriptive statistics (for continuous variable), presented per anatomic site and for:

- each of the six combinations of injected peptide/radioactivity dose range
- each of the two peptide mass dose ranges
- each of the three radioactivity dose ranges

Also, for comparing lesions detection between ^{68}Ga -OPS202 and SOT, the following analyses will be performed:

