- Number of subjects having lesions detected by ^{68}Ga -OPS202 when no lesions is detected by SOT (so called “False Positive” lesions, although in this instance, without histology, this determination is equivocal), in each of five anatomic sites (Primary site of GEP-NET, Lymph nodes, Liver, Axial/appendicular skeleton (Bones), Lungs).
- Number of subjects having lesions detected by SOT when no lesions is detected by ^{68}Ga -OPS202 (so called “False negative” lesions, although in this instance, without histology, this determination is equivocal), in each of five anatomic sites (Primary site of GEP-NET, Lymph nodes, Liver, Axial/appendicular skeleton (Bones), Lungs).

Individual values of number of lesions detected by ^{68}Ga -OPS202 and difference with number of lesions detected by SOT will be listed by subject, by anatomic site and by visit for both types of assessment (PET/CT and PET),

- d) The primary and secondary endpoints will also be evaluated on a radioactivity dose/kg of body weight.

For each subject's visit, the radioactivity dose/kg (in MBq/kg) will be computed using following formula:

$$\text{Radioactivity dose/kg} = \frac{\text{Injected radioactivity dose at visit (MBq)}}{\text{Patient's weight at visit (kg)} *}$$

*In case subject's weight is not available at visit, last weight value will be used.

First, as a preliminary step, a boxplot will be drawn in order to describe subjects' weight at Visit 2, for each of 6 combinations of injected peptide/radioactivity dose range.

The following efficacy criteria will be analysed:

- Primary criterion: Relative lesion count (overall and per each of the five anatomic sites)
- Secondary criteria: Image quality (tumour-to-background ratio for each of the four organs, quality score), lesion SUV_{max} in each of the four organs, absolute number of lesions in each of the five anatomic sites, difference between number of lesions detected by ⁶⁸Ga-OPS202 and number of lesions detected by SOT.

As graphical analysis of the radioactivity dose/kg, the following plots will be performed (plot of individual values) with both peptide dose ranges shown by using two different symbols:

- Scatterplot of radioactivity dose/kg x relative lesion count, per organ and overall
- Scatterplot of radioactivity dose/kg x tumour-to-background ratio, for each of the four organs (Lymph nodes, Liver, Axial/appendicular skeleton (Bones), Lungs)
- Scatterplot of radioactivity dose/kg x quality score

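### The image-quality score is a preference against an opponent fixed by arm, so its peptide summaries can show a peptide difference when none exists

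*SAP*

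**What the plan says.** SAP 3.2.1.2 a), Qualitative measure, has each blinded reader compare the Visit 2 and Visit 3 scans of the same subject: "He/she will note which of the pair provides superior images based on overall image quality and lesion count, attributing a score for each assessment". The preferred scan scores 1 and the other 0. For ties, "In case of equal quality, both assessments will have a score of" 1.

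On reporting: "Quality score will be analysed using descriptive statistics (frequencies and percentage), presented for" the six combinations, the two peptide ranges and the three radioactivity ranges, separately for readers A and B. The two readers' scores are also summed for the six combinations. In addition, "which scan do reader prefer and reason for selecting scan 2 or 3 will be listed per reader".

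Part d) of the same section repeats the endpoints on an MBq/kg basis and includes this one: "Secondary criteria: Image quality (tumour-to-background ratio for each of the four organs, quality score". It plans a "Scatterplot of radioactivity dose/kg x quality score", "with both peptide dose ranges shown by using two different symbols". It also plans tables by MBq/kg quartile, and by quartile crossed with peptide range (eight cells).

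On use, the choice of dose range "will be based on the provided descriptive statistics for all secondary and exploratory efficacy endpoints, in addition to primary endpoint".

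Protocol 6.1.1 (also Table 4 in 3.3) fixes the pairs:

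| Arm | Visit 2 | Visit 3 | Scan with more radioactivity |
|---|---|---|---|
| A | 5-20 µg, 40-80 MBq | 30-45 µg, 100-140 MBq | high peptide |
| B | 5-20 µg, 100-140 MBq | 30-45 µg, 160-200 MBq | high peptide |
| C | 5-20 µg, 160-200 MBq | 30-45 µg, 40-80 MBq | low peptide |

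**The concern.** A 1 or 0 from a paired comparison is not a measurement on a common scale. It says only that a scan beat, tied with or lost to one particular other scan. Pooling such scores by peptide range treats them as if every scan had met the same opposition. Here the high-peptide scan has the radioactivity advantage in two arms out of three, so a pure preference for more radioactivity can appear as a preference for more peptide.

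This matters because the score is among the statistics that may inform the peptide range, and because no test or interval is planned (SAP 3.1.5, 3.2.1.1) that would prompt a second look. Protocol 1.5 presumes that peptide dose in this range is not a factor in diagnostic efficacy. A false peptide pattern would bear directly on that premise.

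**Working it through.** **Counts.** 3 arms × 8 subjects × 2 scans = 48 scans: 8 per combination, 24 per peptide range, 16 per radioactivity range. These are the plan's own figures. SAP 2.1.2 excludes by subject, so pairs in the per-protocol set are complete.

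**Assumptions.** No peptide effect. qA, qB and qC are the probabilities that the scan with more radioactivity is preferred in each arm. The documents give no values, so a range is shown. Where qA and qB are set, qC follows from a Bradley-Terry model: logit qC = logit qA + logit qB.

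**Peptide percentages, no ties.**
- Low = [(1−qA) + (1−qB) + qC]/3
- High = [qA + qB + (1−qC)]/3
- Gap = [2(qA + qB − qC) − 1]/3

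For qA = qB = 0.8 the odds are 4 × 4 = 16, so qC = 16/17 = 0.94. Low = (0.2 + 0.2 + 0.941)/3 = 44.7%; high = (0.8 + 0.8 + 0.059)/3 = 55.3%.

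| Case | Low v high peptide |
|---|---|
| Plateau: qA = qC = 1, qB = 0.5 | 50 v 50% |
| qA = qB = 0.6 | 49.7 v 50.3% |
| qA = 0.9, qB = 0.6 | 48 v 52% |
| qA = qB = 0.8 | 45 v 55% |
| qA = qB = 0.9 | 40 v 60% |
| Unanimous: all q = 1 | 33 v 67% (8/24 v 16/24) |

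The sampling SD of the gap is √(8 × 4 × Σq(1−q))/24. At qA = qB = 0.8, Σq(1−q) = 0.16 + 0.16 + 0.055 = 0.375, giving 14 points. Under the plateau it is 12 points.

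**Six-combination table.** At 100-140 MBq the low-peptide cell (arm B) faced 160-200 MBq and has expectation 1−qB. The high-peptide cell (arm A) faced 40-80 MBq and has expectation qA. The unanimous case gives 0 v 100%. The plateau with arm B split evenly gives 50 v 100% there, and 100 v 50% at 160-200 MBq. Read by arm, the same cells are correct.

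**Quartile by peptide table.** Simulated trials of 24 subjects, with doses uniform within their ranges, weight uniform over 50-110 kg (the limits in Protocol 4.1; the shape is assumed) and quartiles taken from the 48 pooled MBq/kg values, about 6 scans per cell. Plateau above 100 MBq, by how arm B is read:

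| Arm B reads | Quartile 2, low v high |
|---|---|
| None tied, split evenly | 34 v 66% |
| Half tied | about 51 v 67% |
| All tied | 66 v 66% |

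With no ties, quartile 4 is 92 v 58%, the opposite direction. The SD of each difference is about 25 points. A gap of 25 points or more appears in about 65% of trials in quartile 2, against about 36% in quartile 3, where almost none is expected.

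**Scatterplot.** In the same split plateau, all 8 high-peptide points from 100-140 MBq lie at 1, and on average 4 of the 8 low-peptide points lie at 0. Both sets span the same possible range, 100/110 = 0.9 to 140/50 = 2.8 MBq/kg. At 160-200 MBq (160/110 = 1.5 to 200/50 = 4.0 MBq/kg) the pattern reverses.

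**Tie rule.** Against half credit, a tie share t in an arm raises both of that arm's cells by t/2.
- Each arm has one cell in each peptide margin, so the peptide difference does not change.
- The radioactivity margins (40-80, 100-140, 160-200 MBq) rise by (tA+tC)/4, (tA+tB)/4 and (tB+tC)/4. Equal tie rates leave contrasts alone: with 25% ties and q = 0.8 in arms A and B, half credit gives 22/50/78% and the SAP rule 35/62.5/90%, each 12.5 points higher.
- Unequal rates do change contrasts. Under the plateau the margins are 0/75/75% if arm B splits and 0/100/100% if it ties.

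**The case against.** The score is explicitly supportive of the tumour-to-background ratio, relative lesion count leads the selection (SAP 3.2.1.1), and nothing is tested. Each reader's preference is listed by subject, and SAP 5 says the six-combination summary of the key secondary variable keeps the arms visible. A careful reader can recover the pairs: ties in an arm equal the Visit 2 ones plus the Visit 3 ones minus n. The peptide gap is nil under a plateau and smaller than its sampling SD at 0.8. The quartile cells are noisy anyway. All of this stands and limits the importance. It does not correct the pooled displays; it only lets someone detect the problem.

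Two stronger readings are tempting, and the documents do not support them.
- A reader might infer that scoring ties 1/1 distorts every percentage. It affects only percentages that contain tied pairs, which then mean preferred or equal. If arm B ties under a plateau, the rule even removes the false gap at 100-140 MBq: 100 v 100%, where half credit gives 50 v 100%.
- A reader might infer that the quartile table misleads under a plateau whatever the readers do. It does so only to the extent that they split rather than tie in arm B, and the SAP allows them to call scans equal. The plateau is itself an assumption: Protocol 1.5 aims for a clear signal over 100-200 MBq, which is not a statement of equal preference.

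**Conclusion.** The point holds, with modest importance. The opponent structure follows from the documents alone: pooling this score by peptide range, by MBq/kg quartile and peptide, or by peptide symbol mixes radioactivity preference into an apparent peptide contrast. So does comparing peptide cells at one radioactivity range without regard to arm. The false difference in the peptide percentages runs from 0 to 33 points, and is about 11 points at 80% preference. That size rests on assumed preference strengths and, without ties, on the Bradley-Terry link between arms. The quartile results also rest on assumed weights and tie rates. The tie rule is a secondary matter: it raises levels, and changes radioactivity contrasts only when tie rates differ between arms. The table templates in SAP Appendix 2 were not available, so nothing is concluded about their labels.

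**What to change.** For this score only:
- Report, for each arm and each reader, the counts Visit 2 better, equal and Visit 3 better. Present the summed-reader table the same way.
- Drop the peptide-range percentages, the quartile by peptide percentages and the peptide symbols in the scatterplot, or state that they are not used for dose selection.
- In the three-range radioactivity summary, show wins, ties and losses separately.

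The cost is SAP wording and table and figure shells. The preferences are already collected, so no new reads or data are needed.
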